## 7.0 SUBJECT AND DONOR HEART DISPOSITION

The number of applicable recipients will be presented for each of the following categories:

- Signing the informed consent
- Transplanted without randomization
- Randomized to DCD Heart Possible arm
- Randomized to SOC Heart Only arm
- Randomized but not transplanted, subject disposition
- Randomized and transplanted with DCD hearts (DCD-mITT population)
- Randomized and transplanted with SOC hearts (SOC-mITT population)
- Transplanted with DCD heart per-protocol (DCD Heart Transplant Recipient Population)
- Transplanted with SOC heart per-protocol (SOC Heart Transplant Recipient Population)

The number and percentage of SOC heart transplanted recipients (SOC1, SOC2, and Total) and DCD heart transplanted recipients who completed the study, who died on study, who discontinued from the study early, both overall and by time period (before day 30, between day 30 and 6 months, and between 6 months and 12 months), and the reason for early discontinuation will also be presented. Re-transplanted patients will be considered as discontinued the study at the time of re-transplantation.

Donor heart disposition and acceptance details will be summarized for all donor hearts in the database using frequencies and percentages for the following categories:

- All donor hearts screened in the database
- Donor hearts transplanted without randomization
- Donor hearts by randomized recipient and by organ type (DBD or DCD)
- Donor hearts dry-run by recipient randomization
- Donor hearts instrumented on the OCS Heart System (mOCS Heart Population)
- Donor hearts instrumented on the OCS Heart System without protocol deviations (OCS Heart Population)
- Donor hearts instrumented on the OCS Heart System that did not meet the WIT limit or were pediatric donors

## **8.0 PROTOCOL DEVIATIONS AND VIOLATIONS**

Protocol deviations will be summarized for the DCD-mITT Heart Transplanted Recipient Population and the SOC-mITT Heart Transplanted Recipient Population (SOC1, SOC2, and Total) by type of deviation and overall using counts and percentages.

Prior to the database lock, protocol violations will be identified and documented based on a review of potential protocol violations. The protocol violations include, but are not limited to, subjects who did not meet key inclusion/exclusion criteria or transplantability criteria for OCS group, and pediatric donor for SOC group. Patients with at least one protocol violation will be excluded from the DCD and SOC Heart Transplanted Recipient Populations but will be included in DCD-/SOC-mITT populations.

## **9.0 DEMOGRAPHIC AND BASELINE CHARACTERISTICS**

Recipient and donor demographic and baseline characteristics will be summarized for the DCD-mITT Heart Transplanted Recipient Population, the DCD Heart Transplanted Recipient Population, the SOC-mITT Heart Transplanted Recipient Population, and the SOC Heart Transplanted Recipient Population. Frequencies and percentages will be presented for categorical variables, and descriptive statistics will be presented for continuous variables.

Recipient non-cardiac medical history at screening will be summarized for the SOC Heart Transplanted Recipient Population, the SOC-mITT Heart Transplanted Recipient Population, the DCD Heart Transplanted Recipient Population, and the DCD-mITT Heart Transplanted Recipient Population using descriptive statistics for continuous variables and frequencies and percentages for categorical variables.

Donor medical history will be summarized for the SOC Heart Transplanted Recipient Population, the SOC-mITT Heart Transplanted Recipient Population, the DCD Heart Transplanted Recipient Population, and the DCD-mITT Heart Transplanted Recipient Population using frequencies and percentages.

Donor heart procurement data will be summarized for the DCD Heart Transplanted Recipient Population and the DCD-mITT Heart Transplanted Recipient Population using frequencies and percentages. Total number of days since recipient was consented until transplanted and total number of days since recipient was placed on waiting list will be summarized for DCD and SOC patients.

## **10.0 OCS PRESERVATION CHARACTERISTICS**

OCS perfusion time and ischemic time will be summarized using descriptive statistics for the DCD Heart Transplanted Recipient Population, the DCD-mITT Heart Transplanted Recipient Population, and the turn-down hearts. Donor heart chemistry data on OCS instrumentation will be summarized by time point (initial OCS instrumentation, and final OCS instrumentation) using descriptive statistics for the DCD Heart Transplanted Recipient Population and the DCD-mITT Heart Transplanted Recipient Population and turn-down hearts.

Device malfunction data will be summarized using frequencies and percentages.

## **11.0 TRANSPLANT CHARACTERISTICS**

Summaries of transplant details for the DCD and DCD-mITT Heart Transplanted Recipient Populations will be presented, using descriptive statistics for continuous variables and frequencies and percentages for categorical variables.

## 12.0 EFFECTIVENESS ANALYSES

All PGD based effectiveness endpoints will be based on the recipient CEC adjudicated primary graft surveillance data.

### 12.1 Primary Effectiveness Endpoint Analyses

The primary effectiveness endpoint is a comparison of survival at the six months post-transplant visit for DCD heart transplanted recipients and standard criteria heart transplanted recipients (SOC1 + SOC2), adjusting for differences in known risk factors. It will be calculated for both the DCD/SOC Heart Transplanted Recipient Populations and the DCD/SOC-mITT Heart Transplanted Recipient Populations, with the comparison of the DCD Heart Transplanted Recipient Population vs. the SOC Heart Transplanted Recipient Population considered the primary analysis. This is a non-inferiority study.

We will adjust for the known donor and recipient risk factors for mortality shown in the list below:

Donor Variables:

- Donor age  $\geq$  55 years
- Ischemic Time  $\geq$  4 hours
- Gender mismatch (female donor to male recipient).

Recipient Variables:

- Recipient age  $\geq$  65 years
- MCS (including LVAD, RVAD, BiVAD, ECMO, TAH, or IABP) prior to transplant
- Mechanical ventilation at time of transplant

The null and alternative hypotheses for the primary endpoint are as follows:

$$H_0: p_{SOC} - p_{DCD} \geq 0.20$$

vs.

$$H_1: p_{SOC} - p_{DCD} < 0.20$$

where  $p_{DCD}$  and  $p_{SOC}$  represent the true survival proportions at the six months follow-up visit for DCD and SOC heart transplant patients, respectively.

The primary analysis of this endpoint will be performed using a linear probability model, with the following terms in the model: (1) treatment; and (2) the known donor and recipient risk factors listed above. Variables that make the model fail to converge (e.g., due to quasi-complete separation of datapoints) will be dropped from the model. The p-value for the test of the null hypothesis will be obtained based on a statistic for the difference (SOC - DCD) in least squares mean proportions for each treatment minus the non-inferiority margin of 0.20 all divided by the standard error of the difference in the least squares mean proportions and assuming an approximate normal distribution. The test will be conducted at the one-sided 0.05 level of significance. Additionally, this endpoint will be summarized by treatment group using counts

and percentages, and an exact (Clopper-Pearson) 95% confidence interval for the percentages will be presented.

Generalized SAS code to implement this analysis is given below:

```
ods output diffss=diffss lsmeans=lsmeans;
proc genmod descending;
  class trt01a (ref='DCD');
  model survival=trt01a riskfactors / dist=binomial link=identity;
  lsmeans trt01a / diff cl alpha=0.1;
run;

data diffss;
  set diffss;
  pvalue=put(probnorm((estimate - 0.20)/stderr), 6.4));
run;
```

Per FDA's request, a sensitivity analysis will be performed to compare the DCD Heart Possible Population vs the SOC Only Population, i.e. (DCD + SOC2) vs SOC1. Also at FDA's request, an additional sensitivity analysis will repeat the primary effectiveness analysis with the same non-inferiority margin but without adjustment for covariates. Finally, assuming the primary analysis results demonstrate non-inferiority of OCS to SOC, a tipping point analysis (without risk factor adjustment) will be performed using the Wald method, in which SOC subjects categorized as having an unsuccessful 6-month survival outcome will be iteratively imputed as having a successful survival outcome. The "tipping point" is the number of SOC subjects needed to be imputed as having successful outcomes in order to no longer reject the null hypothesis of inferiority.

An additional analysis of the primary endpoint will evaluate pooling by recipient investigational site. This analysis will be performed on observed data for both the DCD/SOC Heart Transplanted Recipient Populations and the DCD/SOC-mITT Heart Transplanted Recipient Populations. A logistic regression model will be fit with all terms included in the primary effectiveness analysis, site, and the interaction of site with treatment. The p-values for site and the treatment by site interaction term in the model will be presented, with statistical significance defined at the  $\alpha = 0.15$  level. Sites with  $\leq 10$  subjects will be pooled for this analysis.

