However, due to potential damage of warm ischemia in the donor and the functional arrest of the heart that may never recover, DCD donors are **not** utilized for adult heart transplantation in the U.S. In contrast, international transplant centers have been successfully transplanting hearts from DCD donors, using the OCS Heart System for resuscitation, preservation and assessment of these hearts prior to transplantation. The OCS Heart System can minimize the detrimental effects of ischemia because it perfuses the donor heart with warm oxygenated blood. It enables the heart to be resuscitated to full beating state, and importantly enables the transplant team to assess metabolic (lactate production) and perfusion parameters of these hearts to determine their suitability for transplantation. These capabilities are critical when using extended criteria and DCD donor hearts to minimize the risks on the recipients receiving these organs.

Currently, the TransMedics' OCS Heart technology is the only portable system available for ex-vivo maintenance of the donor heart in a metabolically active and beating state.

Specifically, with regard to the challenges posed by DCD donor hearts noted above, the OCS Heart System offers the following advantages and capabilities:

- Resuscitation of the DCD heart into beating physiologic state ex-vivo to enable for the assessment of the donor heart's viability.
- Reduction of the time-dependent ischemic injury to the donor hearts during preservation, thus eliminating significant logistical and geographical barriers to heart transplantation that currently exist with cold storage preservation.
- Optimization of donor heart ex-vivo environment by optimizing oxygen and substrate delivery, while also replenishing key hormones and nutrients that are depleted due to the brain-dead condition in the body of the donor, which would negatively impact cardiac function if not replenished.
- Assessing the adequacy of the perfusion and metabolic condition of the donor heart utilizing standard lactate levels to allow physicians to judge the suitability of the organ for transplantation using the standard criteria that physicians currently use when harvesting

the organ from the donor, thus substantially minimizing the risk of transplanting poor hearts into recipients.

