7.5.1. Donor Heart Acceptance/Rejection for Transplantation after OCS Preservation

Donor hearts preserved on the OCS should have stable parameters throughout perfusion after initial stabilization period (defined as the time period during which perfusion is initiated and primary parameter adjustments are made).

Accept for Transplantation

Donor hearts preserved on the OCS Heart System to be maintained within the following target ranges:

- Stable or downward trending lactate after initial adjustments of the OCS Heart perfusion parameters to achieve adequate perfusion to the donor heart
- Stability of OCS Heart Perfusion Parameters within range:
 - AOP 40-100 mmHg.
- Transplanting surgeon and/or heart failure cardiologist must clinically accept the OCS perfused donor heart for transplantation.

Reject for Transplantation

- Transplanting surgeon and/or heart failure cardiologist clinically unsatisfied with donor heart condition/performance on the OCS Heart System at final evaluation.
- Unstable and rising arterial lactate despite maneuvers to optimize perfusion parameters.

Note: certain donor hearts may require perfusion with parameters outside of these guidance ranges. Acceptance for transplantation should be primarily based on an acceptable lactate trend.

Any decision to turndown hearts after preservation and assessment on OCS Heart System should be documented on the appropriate CRF. Samples should be sent to the central core lab for assessment of any inherent cardiac pathology that was not diagnosed at retrieval of the donor heart.

8. TRANSPLANT, IMMEDIATE POST-OPERATIVE AND LONG-TERM FOLLOW-UP FOR DCD HEART TRANSPLANTED RECIPIENTS ONLY

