8.1. Transplant Details

The following information concerning the transplant procedure will be collected:

- The organ recipient unique post-transplant patient identifier
- Warm ischemic time as defined in this protocol

- Total cross clamp duration in minutes (from donor cross-clamp application to removal of cross-clamp in the recipient)
- Pre-OCS cold ischemia time (time from donor cross clamp until start of perfusion on OCS)
- Post-OCS cold ischemia time (time from heart flush on OCS until aortic cross-clamp removal in the recipient)
- Any surgical complications encountered during surgery.

8.2. Post-transplant Functional Assessments Day 0 – Day 30

- Heart PGD Surveillance in the first 24 hours
- Initial use of Mechanical Circulatory Support in the first 72 hours
- Inotropic Support for first 24 hours from T0 to T24 hours after ICU admission
- Echocardiogram results within the first 24 hours post-transplant (if available) starting from ICU admission
- Right Heart Catheter Data (not required; data collected only if performed as part of institution's standard of care)
- Initial Post-Transplant ICU Stay
- Initial Post-Transplant Hospital Stay
- Patient and Graft Survival at Day 30 will be assessed.
- Serious Adverse Events: All SAEs will be collected for the first 30 days post-transplant. SAEs will be followed until the investigator designates the event to be either resolved or its effect on the patient's condition stabilized.

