10.3. Statistical Analysis

10.3.1. Primary Endpoint

The primary endpoint is a comparison of survival at 6 months for DCD heart transplanted recipients and standard criteria heart transplanted recipients (**SOC1 + SOC2** as defined in [Section 6.4](#)), adjusting for differences in risk factors. This is a non-inferiority study.

Risk Factors

We will adjust for the known donor and recipient risk factors for mortality shown in the list below²:

² Cardiac Donor Risk Factors Predictive of Short-Term Heart Transplant Recipient Mortality: An Analysis of the United Network for Organ Sharing Database. Trans Proc. 2015 Dec; 47(10): 2944-2951., Heart Transplant Survival based on Recipient and Donor Risk Scoring: A UNOS Database Analysis, ASAIO J., 2016; 62:297-301. Report from the American Society of Transplantation Conference on Donor Heart Selection in Adult Cardiac Transplantation in the United States. Am.J.Transplant, 2017; 17:2559-2566

Donor Variables:

- Donor Age \geq 55 years
- Gender mismatch (female donor to male recipient).

Recipient Variables:

- Age \geq 65
- LVAD, ECMO or IABP prior to transplant

For continuous baseline characteristics, two-sided, two-sample t-tests will be used to test for a difference in means between treatment groups. For categorical baseline characteristics, the chi-square test will be used to test for a difference in proportions between treatment groups. We will adjust the analysis of the primary endpoint for any of these baseline characteristics for which there is a statistically significant difference (p -value < 0.15) between the treatment groups.

The null and alternative hypotheses for the primary endpoint are as follows:

$$H_0: p_{SOC} - p_{DCD} \geq 0.20$$

vs.

$$H_1: p_{SOC} - p_{DCD} < 0.20$$

where p_{DCD} and p_{SOC} represent the true survival proportions at 6 months for DCD and SOC heart transplant patients, respectively.

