### **3.5 Changes to the Protocol-Specified Analyses**

The protocol proposed stopping enrollment once the DCD heart transplanted recipients enrollment target (N=90) was met. Further, if the enrollment target in the SOC heart transplanted recipient population had not been met, a propensity-score-matched subset of subjects from the UNOS database was proposed to supplement the set of subjects in the SOC Heart Transplanted Recipient Population at the time of the last DCD transplant. However, in communications with FDA it became clear that FDA strongly preferred prospective enrollment of 90 SOC subjects rather than the propensity matched approach outlined in the protocol. Therefore, the statistical analysis will be performed using the 90 DCD and 90 SOC subjects that were prospectively enrolled without propensity-matched subjects from UNOS.

The protocol stated that the analysis of the primary effectiveness endpoint would be adjusted for known donor and recipient risk factors (defined in section 12.1) for mortality, and any of the baseline and demographic characteristics identified as potential risk factors for which there is a statistically significant difference between the treatment groups. This SAP clarifies that the primary effectiveness analysis will be adjusted for known donor and recipient risk factors for mortality, but not for baseline and demographic characteristics identified as potential risk factors.

The protocol stated that statistical testing will be performed for the comparisons of recipient demographics and baseline characteristics and of patient survival at 6 months for the following groups: SOC1 vs SOC2, DCD Heart vs SOC1, DCD Heart vs SOC2. Only summary statistics will be provided for those comparisons.

[figure not shown]

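### The SAP's primary model adjusts for ischemic time of 4 hours or more, a post-treatment covariate that is not in the protocol's list or the SAP's change log; the likely bias is modest and against the DCD arm

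*SAP*

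**What the plan says.** Protocol 10.3.1 ("We will adjust for the known donor and recipient risk factors for mortality shown in the list below") names four factors: donor age 55 or over, female donor to male recipient, recipient age 65 or over, and LVAD, ECMO or IABP before transplant.

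SAP 12.1 names six. It adds "Ischemic Time $\geq$ 4 hours", classed as a donor variable, and mechanical ventilation at transplant. It also widens pre-transplant support to RVAD, BiVAD and TAH. All enter the primary model unless one prevents convergence.

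SAP 3.5, the change log, says that under the protocol the analysis "would be adjusted for known donor and recipient risk factors (defined in section 12.1) for mortality". The SAP's list is thus credited to the protocol. The only covariate change that 3.5 records is a removal: the potential risk factors are no longer adjusted for.

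The hypotheses in both documents concern the true 6-month survival proportions of the two groups, with a margin of 0.20 at one-sided 0.05.

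**The concern.** The log gap matters because this is the deciding model. From SAP 3.5 a reader would conclude that the adjustment narrowed, when its fixed list grew.

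Ischemic time also differs in kind from the other five covariates, which are fixed before the heart is preserved. Apart from donor warm ischemia, which is specific to DCD hearts and capped at 30 minutes in the primary population, every interval in Protocol 8.1 starts at or after donor cross-clamp. Its length depends partly on the preservation method. Protocol 1.1 lists among the device's advantages "Reduction of the time-dependent ischemic injury to the donor hearts during preservation". Adjusting for ischemic time therefore conditions on part of the claimed mechanism. The model then compares the groups as if equal shares of hearts had passed 4 hours, which is not the comparison in the hypotheses.

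**Working it through.** **Which time counts.** Protocol 8.1 records "Pre-OCS cold ischemia time (time from donor cross clamp until start of perfusion on OCS") and a matching post-OCS cold interval. The overall interval is named separately and is not called ischemia: "Total cross clamp duration in minutes (from donor cross-clamp application to removal of cross-clamp in the recipient"). SAP 10.0 also separates the two: "OCS perfusion time and ischemic time will be summarized using descriptive statistics". Both favour cold time only for an OCS heart. These intervals sit under a Section 8 heading that ends "LONG-TERM FOLLOW-UP FOR DCD HEART TRANSPLANTED RECIPIENTS ONLY", so the source of the SOC value is not stated there. The table shells and eCRFs were not available and may define the term.

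**The plan's own figure.** Inputs from SAP 3.4: SOC 93%, DCD 85%, margin 0.20, one-sided 0.05, power 80%.
- Variance sum: 0.93×0.07 + 0.85×0.15 = 0.1926.
- n = (1.645 + 0.842)² × 0.1926 / (0.20 − 0.08)² = 82.7, so 83 per group against the stated 84.
- At 90 per group the SE is √(0.1926/90) = 0.0463, and power is Φ(0.12/0.0463 − 1.645) = 82.9%.
- Exact enumeration of the unadjusted Wald test gives power 82.6%. At 93/73, where the true difference equals the margin, it gives size 5.7%.

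**Shift from the term.** In an additive model, adjusted difference = (pSOC − pDCD) + b × (SOC share ≥4 h − DCD share ≥4 h), where b is the survival loss at 4 hours or more. The documents give neither b nor the shares, so these are assumptions: b of 0–10 points, and the shares shown below.
- DCD 2%, SOC 15%, b = 0.10: 0.10 × 0.13 = +1.3 points.
- DCD 5%, SOC 20%, b = 0.10: 0.10 × 0.15 = +1.5 points.

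A positive shift counts against DCD. Hand check at 1.5 points: Φ(0.105/0.0463 − 1.645) ≈ 73%.

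**Simulation.** 90 per group, marginal survival held at 93/85 (power) and 93/73 (size), least squares with robust SE, treatment plus this term, 20,000 runs:

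| Share ≥4 h, DCD / SOC | b (points) | Mean estimate at true 0.08 | Power | Size |
|---|---|---|---|---|
| 2% / 15% | 0, 5, 10 | 0.081, 0.087, 0.093 | 80%, 78%, 75% | 5.5%, 4.2%, 3.4% |
| 5% / 20% | 0, 5, 10 | 0.080, 0.088, 0.095 | 81%, 78%, 74% | 5.6%, 4.2%, 3.1% |
| 5% / 30% | 0, 5, 10 | 0.080, 0.093, 0.105 | 80%, 73%, 67% | 5.6%, 3.5%, 2.0% |

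A binomial identity-link fit with the SAP's drop rule, for SOC shares of 15–20%, gave power 75–81% and size 3–5%. It dropped the term in 8–39% of runs, though how often depends on how non-convergence is flagged and SAS may differ. At 93/85 the verdict differed from the model without the term in about 2–9% of trials across the two fits.

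**If the OCS run counted.** Protocol 2.3.2 reports OCS times of 245, 257 and 260 minutes in one series and a mean of 302 (range 210–410) in another, so most DCD hearts would pass 240 minutes. I assumed 90–95% of DCD against 15–20% of SOC. The shift reverses: −0.7b to −0.8b, or 3.5–8 points in favour of DCD for b of 5–10 points. Size becomes 12–24% by least squares, and 7–20% by the identity-link fit with the drop rule. With b = 0 the estimate stays at 0.08 but power falls to 57–62% (identity link: 70–77%). That loss is collinearity with treatment, not a change in what is estimated.

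**The case against.** **The stronger reading.** A reader might infer that the term makes false non-inferiority more likely. The documents do not support that. It requires time on the OCS to count as ischemic, and Protocol 8.1 and SAP 10.0 both point the other way. On the cold-time reading the term is conservative, and size falls below the 5.7% of the model without it. Nor can one say that the plan leaves the term undefined, since the table shells and eCRFs were not available.

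**Confounder or mediator.** The comparison is as-treated, with risk adjustment built in (SAP 3.1), so the crude difference is not self-evidently the target. By fixing marginal survival, the simulation would make any imbalanced prognostic covariate look like drift. For cold-stored hearts, ischemic time also reflects distance and logistics. This stands in part: the simulation does not separate the two roles, and the distinction rests on timing. An imbalance that exists before preservation is confounding, which adjustment should remove. One that the preservation method partly creates belongs to the effect under test.

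**Safeguards.** The SAP plans an unadjusted analysis at the same margin, a comparison by randomized group (also without risk-factor adjustment), an unadjusted tipping-point analysis, and Kaplan-Meier differences at 180 days with 90% intervals. A verdict driven by this term would be visible. None of these decides the trial.

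**Direction of the remedy.** On the favoured reading, removal takes out a term that works against the device. That stands and must be disclosed.

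**Conclusion.** The concern holds in a limited form. That the term is absent from the protocol's list, unrecorded in SAP 3.5 and part of the deciding model needs no assumption. That it is post-treatment follows from the intervals in Protocol 8.1.

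The size rests wholly on assumed shares and effects. Under the favoured reading the bias is modest and conservative: at most about 1.5 points when 15–20% of SOC hearts pass 4 hours, or 0.10 × 0.25 = 2.5 points if 30% do. Power can fall below the stated 80%. With no survival effect, or equal shares, there is no shift. This should be corrected before hard-lock, but it does not undermine the trial.

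**What to change.** Before hard-lock, while SOC 6-month survival is still blinded to the statistical group (SAP 3.3):

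1. Limit the primary model to covariates fixed before preservation.
2. Move ischemic time to one labelled sensitivity model. State which Protocol 8.1 intervals count for an OCS heart, and where the SOC value comes from and how it is measured.
3. In SAP 3.5, record with reasons every departure from the protocol's list: ischemic time, mechanical ventilation and the wider pre-transplant support definition.
4. Report the model with ischemic time beside the primary result.

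No new data are needed and the sample size does not change. The cost is a late change to the primary covariate set, after enrollment, in an open-label trial. On the favoured reading it slightly favours the device, and the primary model loses adjustment for a known risk factor among cold-stored hearts. SAP 3.5 should state both, and item 4 lets a reader see the effect.
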